³ Only applicable for females of childbearing potential. A urine pregnancy test is sufficient. A serum pregnancy test instead of a urine pregnancy test should only be considered if required by country, local or ethics committee regulations.

⁴ One diary card for unsolicited AEs up to 30 days post vaccination

⁵ Subject will be instructed to contact their study site immediately if he/she manifests any symptoms he/she perceives as serious and, in case of pregnancy for women of childbearing potential

⁶ Subjects will be asked to mail the diary cards 30 days after Visit 2 if their Month 3 contact will be by phone or to bring along their diary card if their Month 3 contact will be a site visit. Operational details will be defined in the SPM

⁷ It is the responsibility of the site to follow up until the diary cards are received

Table 5 Intervals between study visits

Interval	Optimal length of interval 1	Allowed interval
Visit 1→Visit 2	60 days (2 months)	49 days - 83 days
Visit 2 → Visit 3/Month 3 Phone contact	30 days (1 month)	30 - 48 days
Visit 2 → Month 8 Phone contact	180 days (6 months)	180 - 240 days
Visit 2 → Month 14* Phone contact	365 days (12 months)	335 –395 days

¹ Whenever possible the investigator should arrange study visits within this interval

*i.e. 12 months post dose 2

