10.7. Analysis of safety

The primary analysis for safety will be based on the TVC.

All analysis may be performed by age group at inclusion in the ZOSTER-006/022 (50-59, 60-69 and ≥ 70 YOA).

When appropriate, tabulations will be presented overall and by time of occurrence related to last vaccination (e.g. using windows such as Days 0-29 and more than 30 days post-vaccination).

The results for the analysis of safety will be tabulated as follows:

- The proportion of subjects with at least one report of an unsolicited AE during the 30-day (Days 0–29) follow-up period after each vaccination classified according to the MedDRA System Organ Class and Preferred Terms will be tabulated, with exact 95% CI.
- The same tabulation will be performed for grade 3 unsolicited AEs and for unsolicited AEs with a relationship to vaccination. The proportion of AEs resulting in a medically attended visit will also be tabulated.
- Total number/percentages of doses (per dose and overall) followed by AEs will be tabulated.
- SAEs and withdrawal due to AE(s) will be described in detail.
- Number of subjects with pIMDs will be tabulated.

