6.3. Analysis of safety

6.3.1. Analysis of safety planned in the protocol

The analysis for safety will be based on the TVC.

All analysis will be performed overall and by age sub-group at vaccination in the ZOSTER-056 (50-59, 60-69, 70-79 and ≥ 80 YOA).

When appropriate, tabulations will be presented overall and by time of occurrence related to last vaccination (e.g. using windows such as Days 0-29 and more than 30 days post-vaccination).

The results for the analysis of safety will be tabulated as follows:

- The proportion of subjects with at least one report of an unsolicited AE during the 30-day (Days 0–29) follow-up period after each vaccination classified according to the MedDRA System Organ Class and Preferred Terms will be tabulated, with exact 95% CI.
- The same tabulation will be performed for grade 3 unsolicited AEs (including SAEs) and for unsolicited AEs with a relationship to vaccination. The proportion of AEs resulting in a medically attended visit will also be tabulated.
- Total number/percentages of doses (per dose and overall) followed by AEs during the 30 days (Days 0-29) follow-up period after each vaccination classified according to the MedDRA System Organ Class and Preferred Terms will be tabulated.
- SAEs will be described in detail in listing for the entire study period.
- Withdrawal due to AE(s) and SAE will be described in detail in listing for the entire study period.
- Number of subjects with pIMDs will be tabulated according to the MedDRA System Organ Class and Preferred Terms for the period during first vaccination up to 30 days post second vaccine dose, after 30 days post second vaccine dose to study end and from first vaccination to study end.

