11. ANNEX 1 STANDARD DATA DERIVATION RULES AND STATISTICAL METHODS

11.1. Statistical Method References

The exact two-sided 95% CIs for a proportion within a group will be the Clopper-Pearson exact CI [Clopper CJ, Pearson ES. The use of confidence or fiducial limits illustrated in the case of binomial. *Biometrika*. 1934;26:404-413].

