11.2.2. Dose number

- The study dose number is defined in reference to the number of study visits at which vaccination occurred. More specifically dose 1 refers to all vaccines administered at the first vaccination visit while dose 2 corresponds to all vaccinations administered at the second vaccination visit even if this is the first time a product is administered to the subject.
- Associated dose: the associated dose for an event (AE, medication,...) is the most recent study dose given before an event. In case the event takes place on the day a study dose is given, the associated dose will be that of the study dose, even if the event actually took place before vaccination. For instance, if an adverse event begins on the day of the study vaccination but prior to administration of the vaccine, it will be assigned to this dose. In case a study dose is not administered and an event occurs after the subsequent study dose (e.g. 2nd study dose), the associated dose of the event will be study dose associated to the subsequent study dose (e.g. dose 2).
- The number of doses for a product is the number of times the product was administered to a subject.
- The incidence per dose is the number of visits with vaccine administered at which an event was reported among all visits with vaccine administered.

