		PHONE CONT M14			

*Age sub-group is based on subject's age at first vaccination

50-59YOA = Subjects aged 50-59 years

60-69YOA = Subjects aged 60-69 years

70-79YOA = Subjects aged 70-79 years

≥80YOA = Subjects aged 80 years and over

HZ/su = Herpes Zoster subunit vaccine

N = Number of subjects who are still in the study up to the visit

Withdrawn = Subject who did not return after the visit

PHC = Phone contact

Template 17 Number and percentage of subjects who received study vaccine doses (Total Vaccinated Cohort)

	HZ/su N =	
Total number of doses received	N	%
1		
2		
Any		

HZ/su = Herpes Zoster subunit vaccine

N = number of subjects in the group or in total included in the considered cohort

n/% = number/percentage of subjects receiving the specified total number of doses

Any = number and percentage of subjects receiving at least one dose

Template 18 Number and percentage of subjects reporting the occurrence of <grade 3> <non-serious><unsolicited adverse events> classified by MedDRA Primary System Organ Class and Preferred Term <with causal relationship to vaccination> <with medically attended visit> within the 30-day (Days 0-29) post-vaccination period (<Total Vaccinated Cohort, Total Vaccinated Cohort - confirmed HZ episode during Zoster-006/022>)

		HZ/su N =			
				95% CI	
Primary System Organ Class (CODE)	Preferred Term (CODE)	n	%	LL	UL
At least one symptom					
Each SOC	At least one PT related to the corresponding SOC				
	Each PT				

HZ/su = Herpes Zoster subunit vaccine

At least one symptom = at least one symptom experienced (regardless of the MedDRA Preferred Term)

N = number of subjects with the administered dose

n/% = number/percentage of subjects reporting the symptom at least once

95% CI = exact 95% confidence interval; LL = Lower Limit, UL = Upper Limit

Template 19 Number and percentage of doses with <grade 3> unsolicited adverse events classified by MedDRA Primary System Organ Class and Preferred Term <with causal relationship to vaccination> <with medically attended visit> within the 30-day (Days 0-29) post-vaccination period (Total Vaccinated Cohort)

		HZ/su			
		N =		95% CI	
Primary System Organ Class (CODE)	Preferred Term (CODE)	n	%	LL	UL
At least one symptom					
Each SOC	At least one PT related to the corresponding SOC				
	Each PT				

HZ/su = Herpes Zoster subunit vaccine

At least one symptom = at least one symptom experienced (regardless of the MedDRA Preferred Term)

N = number of administered doses

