n/% = number/percentage of doses with the symptom

95% CI= exact 95% confidence interval; LL = Lower Limit, UL = Upper Limit

Template 20 Global summary of <grade 3> <non-serious><unsolicited adverse events> <with causal relationship to vaccination> <with medically attended visit> reported within the 30-day (Days 0-29) post-vaccination period (Total Vaccinated Cohort)

	HZ/su
Number of subjects with at least one unsolicited symptom reported	
Number of doses followed by at least one unsolicited symptom	
Number of unsolicited symptoms classified by MedDRA Preferred Term*	
Number of unsolicited symptoms reported**	

HZ/su = Herpes Zoster subunit vaccine

* Symptoms reported by a subject after a given dose and classified by the same Preferred Term are counted once

** Symptoms reported by a subject after a given dose and classified by the same Preferred Term and the same start date of the event, are counted once

Template 21 Number and percentage of subjects reporting the occurrence of <potential Immune-Mediated Diseases> <serious adverse events> classified by MedDRA Primary System Organ Class and Preferred Term <with causal relationship to vaccination> reported <from first vaccination up to 30 days post last vaccination dose> <after 30 days post last vaccination dose up to study end><from first vaccination until study end > (<Total Vaccinated Cohort, Total Vaccinated Cohort - confirmed HZ episode during Zoster-006/022>)

		HZ/su N =				
					95% CI	
Primary System Organ Class (CODE)	Preferred Term (CODE)	n*	n	%	LL	UL
At least one symptom						
Each SOC	At least one PT related to the corresponding SOC					
	Each PT					

HZ/su = Herpes Zoster subunit vaccine group

At least one symptom = at least one symptom experienced (regardless of the MedDRA Preferred Term)

N = number of subjects with the administered dose

n/%= number/percentage of subjects reporting the symptom at least once

95% CI = exact 95% confidence interval; LL = Lower Limit, UL = Upper Limit

n* = number of events reported (only required for CTRS posting)

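### The text promises doses followed by AEs both by dose and overall, but Templates 19 and 26 show one pooled-dose block, with an exact CI that treats a subject's two doses as independent

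*SAP*

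**What the plan says.** **Text.** In Protocol 10.7 the dose-level item reads "Total number/percentages of doses (per dose and overall) followed by AEs will be tabulated". The dose bullet of SAP 6.3.1 starts the same way, "Total number/percentages of doses (per dose and overall) followed by AEs", and adds the Days 0-29 window and the SOC/PT classification. Neither bullet asks for a confidence interval. The primary objective (Protocol 2.1, SAP 3.1) concerns safety after each dose.

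**Templates.** Template 19 is titled "Number and percentage of doses with <grade 3> unsolicited adverse events", and Template 26 is its by-age version. These are the only SOC/PT tables that count doses. Each has one n, %, LL, UL block (repeated by age sub-group in Template 26), with the footnotes "N = number of administered doses" and "n/% = number/percentage of doses with the symptom". Grade, causality and medical attendance are bracketed options in the titles; dose number is not. Templates 20 and 27 also give one pooled count of doses. Only individual listings carry a dose field.

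**Definitions.** SAP 11.2.2 defines the incidence per dose as vaccination visits with an event out of all vaccination visits, which is a pooled figure. The same section assigns events to doses: "the associated dose for an event (AE, medication,...) is the most recent study dose given before an event". On intervals, SAP 11.1 states "The exact two-sided 95% CIs for a proportion within a group will be the Clopper-Pearson exact CI".

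**Changes.** SAP 9 lists four changes from the planned analyses. Dropping a split by dose is not one of them.

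**The concern.** If the tables are programmed as drawn, the report would give one AE rate over all doses where the text leads a reader to expect a rate after each dose and a total. A pooled rate can hide a difference between doses. With equal numbers of each dose, rates of 15%/15%, 20%/10% and 25%/5% after Dose 1/Dose 2 all print as 15%. That sits badly with an objective worded by dose.

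The interval is a separate and smaller matter. Clopper-Pearson assumes independent records. On a 0, 2-month schedule most records come in pairs from one person, and no passage adjusts for this. If someone who reports an event after Dose 1 is more likely to report one after Dose 2, the printed limits are too close together.

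**Working it through.** **1. The display.** The documents give no figure to reproduce here, so the passages are set side by side.

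| Place | Per dose | Overall |
|---|---|---|
| Protocol 10.7, SAP 6.3.1 | promised | promised |
| Templates 19, 26 | no column, row or option | one pooled block |
| SAP 11.2.2 | defined as pooled over visits | not defined separately |

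One vaccine is given per vaccination visit, so the SAP 11.2.2 denominator is the number of administered doses, as in Templates 19 and 26. On that reading *per dose* and *overall* are the same number, and naming both has no purpose. On the other reading (Dose 1, Dose 2, total) the templates are incomplete.

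**2. The interval.**

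*Inputs from the documents:* two doses per subject; 2,109 subjects aged 80 or over and 3,349 aged 70-79 (SAP 9); at most 14,550 subjects (Protocol 10.3); two-sided 95% Clopper-Pearson (SAP 11.1); one decimal printed (SAP 11.3).

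*Assumptions, not in the documents:* event rate p per dose, the same after both doses; within-subject correlation rho; every subject given both doses unless stated.

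*Variance.* With N pooled doses in pairs, the variance of the proportion is p(1-p)(1+rho)/N. Clopper-Pearson reflects p(1-p)/N. The interval is therefore too narrow by a factor of about sqrt(1+rho): 1.05, 1.14 and 1.22 at rho 0.1, 0.3 and 0.5.

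*Exact coverage.* The number of doses with an event has generating function (p00 + p10 z + p11 z²)^S2 × (1-p+pz)^S1. Here p11 = p² + rho p(1-p), p10 = 2(p-p11), p00 = 1-p10-p11, and S2 and S1 are the numbers of subjects with two doses and one dose. Coverage is the probability of all counts whose Clopper-Pearson interval on 2×S2+S1 doses contains p.

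| Case | rho 0 | 0.1 | 0.3 | 0.5 |
|---|---|---|---|---|
| p 10%, 2,109 subjects | 95.2% | 94.1% | 91.7% | 89.3% |
| p 10%, 14,550 subjects | 95.2% | 94.0% | 91.7% | 89.3% |
| p 30%, 2,109 subjects | 95.3% | 94.1% | 91.8% | 89.4% |
| p 10%, 2,109 subjects, 80% given Dose 2 | 95.2% | 94.2% | 92.1% | 90.0% |
| p 0.05%, 2,109 subjects | 97.9% | 97.3% | 96.3% | 95.3% |
| p 0.05%, 14,550 subjects | 95.2% | 94.1% | 91.7% | 89.3% |

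At rho of zero or below there is no shortfall. For a rare term in a small sub-group there is none either, because the exact method is conservative there; in the full cohort that protection is gone.

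*Limits.* Adjusted limits put x/(1+rho) and N/(1+rho) into the Clopper-Pearson formula. At p 10% and rho 0.3:

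| Doses with event / doses | As planned | Adjusted | Shift, lower / upper (points) |
|---|---|---|---|
| 422 / 4,218 | 9.115-10.950 | 8.993-11.089 | 0.12 / 0.14 |
| 670 / 6,698 | 9.295-10.747 | 9.197-10.855 | 0.10 / 0.11 |
| 2,910 / 29,100 | 9.658-10.350 | 9.610-10.400 | 0.05 / 0.05 |

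The largest shift with rho up to 0.5 is 0.32 point (p 30%, rho 0.5, 2,109 subjects). At p 1%, rho 0.3 and 14,550 subjects, both versions print as 0.9-1.1.

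*Unequal rates.* If the rates p1 and p2 differ and p is their mean, p1(1-p1) + p2(1-p2) = 2p(1-p) - (p1-p2)²/2. A dose difference therefore offsets the shortfall slightly: for 15% and 5% the sum is 0.175 instead of 0.180.

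**The case against.** The best defence is SAP 11.2.2. Its incidence per dose is the fraction that Templates 19 and 26 display, so the authors may regard the promise as met. That stands as a possible reading, and it makes this less than a plain contradiction. It does not settle the matter, because the bullet already counts doses and still names two figures.

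The second defence is that SAP 10 and SAP 13 leave the final list of tables, and the adaptation of titles and footnotes, to the TFL table of contents. That document is not available here and could list Template 19 run by dose. This also stands. However, SAP 13 speaks of titles, footnotes and minor edits, whereas a split by dose changes columns and denominators.

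A reader might infer that dose-specific results were dropped and will be missing from the report. The documents do not show that: the operative text still commits to them, and the silence of SAP 9 fits equally well with nothing having been dropped. A reader might also infer that the interval undermines the safety conclusions. It does not: SAP 7 makes every analysis descriptive, no decision rests on these limits, and both rho and the rates used here are assumed. Nor does the problem reach the subject-level intervals in Templates 18 and 25, where each subject counts once.

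**Conclusion.** The point holds as a gap between text and templates that needs reconciling. As drawn, Templates 19 and 26 do not show AE rates after Dose 1 and Dose 2 separately, and the one definition that would excuse this makes the promised pair of figures redundant. How firm this is depends on the unseen table of contents.

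The interval is wrong in principle for pooled doses whenever rho is positive, and small in practice. Coverage is about 94%, 92% and 89% at rho 0.1, 0.3 and 0.5 under the stated assumptions, and limits move by no more than about 0.3 point for rho up to 0.5. The case for a change rests mainly on the display.

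**What to change.** In Templates 19 and 26, show Dose 1 and Dose 2 separately, with N the number of subjects given that dose. Each subject then counts once and Clopper-Pearson is valid. Keep an overall-doses column with n and % only; if an interval is wanted there, use a subject-clustered one and name it in SAP 11.1. Reword the incidence-per-dose definition in SAP 11.2.2 to match. If the TFL table of contents already lists per-dose runs, say so in SAP 6.3.1 and correct only the overall interval.

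Programming is modest. The associated dose is already derived, and with an allowed Visit 1 to Visit 2 interval of "49 days - 83 days" (Protocol Table 5) the two Days 0-29 windows do not overlap.

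The cost is wider tables and wider single-dose intervals. At a 10% rate these are 8.8-11.4% instead of 9.1-11.0% with 2,109 subjects, 9.0-11.1% instead of 9.3-10.7% with 3,349, and 9.5-10.5% instead of 9.7-10.4% with 14,550.
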